### **3. Study Design**

- 3.1. This RCT will be performed at the University of New Mexico Hospitalits affiliated clinics and the University of Utah and its affiliated clinics. The study design was chosen as the gold standard for determining cause and effect; it is methodologically strong and feasible for our research questions. RCTs minimize bias such as that related to treatment assignment (e.g., selection bias and confounding).

**PROTOCOL TITLE:** Effect of immediate versus standard postpartum insertion of the contraceptive implant on breastfeeding outcomes

The two study groups will include women randomized to immediate (within 24 hours postpartum) versus standard (4-6 weeks postpartum) ENG implant insertion. The primary study endpoint is any breastfeeding at eight weeks postpartum; we will also measure breastfeeding continuation at 2, 4, 8, 12 and 24 weeks postpartum. Participants will be pregnant women 13 years old and older, who desire the ENG implant as a postpartum contraceptive and are willing to be randomized to immediate implant insertion (within 24 hours postpartum) versus standard insertion (4-6 weeks postpartum). A total of 150 participants, 75 in each group, will be enrolled to ensure adequate power to determine the primary outcomes, after anticipated loss to follow up.

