**5. Number of Subjects**

5.1 NA

PROTOCOL TITLE: Effect of immediate versus standard postpartum insertion of the contraceptive implant on breastfeeding outcomes

5.2. This is a multi-site study. Through the University of New Mexico Hospital, its affiliated clinics and the University of Utah and its affiliated clinics. We will recruit up to 200 participants between both study sites.

5.3. Up to 200 participants will be enrolled, with a goal of 75 in each group, to ensure adequate power to determine the primary outcome, after anticipated loss to follow up.

This study is a non-inferiority trial designed to demonstrate that immediate postpartum insertion of the ENG implant is non-inferior to standard ENG implant insertion with respect to the proportion of women who discontinue breastfeeding by 8 weeks after delivery. Discontinuation of breastfeeding under the current treatment, standard insertion, is expected to be 30% based on previous studies (10, 15). To achieve 80% power with a 1-sided Type 1 error of 5% utilizing the Z test (unpooled), 62 participants are required in each group for a total of 124. Accounting for expected loss to follow up of 20%, the total number of participants required is 149, rounded to 150. We intend to enroll up to 200 participants due to unanticipated loss to follow up, so this should ensure that we have enough data for data analysis.

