## 13.Data Analysis

13.1 We will conduct a primary analysis per protocol and a secondary analysis per intention to treat. The rationale behind this strategy is to analyze both approaches and examine the result for consistency. A Repeated measures ANOVA analysis will be used for continuation of breastfeeding. To evaluate secondary outcomes between the two

**PROTOCOL TITLE:** Effect of immediate versus standard postpartum insertion of the contraceptive implant on breastfeeding outcomes

groups we will use the T-test, Wilcoxon Rank Sum test, Chi-squared test, or Fisher's exact test as appropriate. Secondary outcomes to be evaluated are to compare time of exclusivity of breastfeeding, mix breastfeeding, factors associated with discontinuing breasts feeding, time of breastfeeding discontinuation and patient satisfaction with postpartum contraception counseling and with timing of placing the implant between both groups. If there are significant differences between treatment groups, multivariable linear (for continuous outcomes) and logistic (for dichotomous outcomes) regression will be utilized in addition to control for confounding.

13.2 This study is a non-inferiority trial designed to demonstrate that immediate postpartum insertion of the ENG implant is non-inferior to standard ENG implant insertion with respect to the proportion of women who fail to breastfeed by 8 weeks after delivery. The failure rate for continuation of breastfeeding under the current treatment, standard insertion, is expected to be 30%.

The following sample size determination and plan for data analysis was developed in conjunction the University of New Mexico Clinical and Translational Science Center (CTSC). The non-inferiority margin for both primary outcomes is 15%, meaning that immediate insertion can be regarded as non-inferior (in terms of breastfeeding continuation) to standard insertion if the difference in rate with immediate insertion is no more than 15% worse than with standard insertion. To achieve 80% power with a 1-sided Type 1 error of 5% utilizing the Z test (unpooled) 62 participants are required in each group for a total 124. Accounting for the expected loss of follow up of 20%, the total subjects 149, round to 150. We intend to enroll up to 200 participants due to unanticipated loss to follow up, so this should ensure that we have enough data for data analysis.

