## **14. Provisions to Monitor the Data to Ensure the Safety of Subjects**

A Data and Safety Monitoring Plan has been developed and will be led by [name] at the University of New Mexico, who is an independent physician. [name] will monitor the study at least quarterly.

The ENG implant is an FDA approved drug, which has a well-established record in breast feeding women. Early implant insertion reflects standard practice in many centers, including the University of New Mexico. The data monitored and reviewed will include enrollment and dropout rates, protocol deviations, review of subject symptoms, and preliminary analysis of the primary outcomes (continuation of breastfeeding at 8 weeks). The reports will include enrollment and dropout rates, protocol deviations, review of subject symptoms, and preliminary analysis of the primary outcomes. The trial will be stopped for a cessation of breastfeeding in more than 70% of the early insertion group in the first 8 weeks. Any additional reports to the IRB will occur in response to specific events adverse events. Any serious adverse event defined as an event requiring re-hospitalization will require re-evaluation of the risk determination and continuation of the study. Adverse event reporting will follow

**PROTOCOL TITLE:** Effect of immediate versus standard postpartum insertion of the contraceptive implant on breastfeeding outcomes

guidelines as proposed by Good Clinical Practice and collected as they occur or are reported by patients. These reports will be compiled for review by the DSMB quarterly; except for serious adverse events which will be reported to the IRB and DSMB within 24 hours of the occurrence. All subjects will have access to clinical care which is not dependent on study participation and will be notified of the availability of that care. All data will be collected for quarterly reporting to the DSMB as well as for final data analysis and reporting. There may be times when we are required by law to share information. However, protected health information (PHI) will not be used in any published reports about this study.

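### Section 13.1 gives repeated-measures ANOVA for continuation of breastfeeding, section 13.2 sets a 15% margin and a Z test, and no sentence says which decides the 8-week primary endpoint

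*Combined protocol and SAP*

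**What the plan says.** Section 3.1 defines the endpoint: "The primary study endpoint is any breastfeeding at eight weeks postpartum". It adds that "we will also measure breastfeeding continuation at 2, 4, 8, 12 and 24 weeks postpartum". Sections 1.2.1 and 7.1 call the same primary outcome continuation of lactation, and section 14 describes the monitoring reports as including "preliminary analysis of the primary outcomes (continuation of breastfeeding at 8 weeks".

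Section 13.1 makes the per-protocol analysis primary and the intention-to-treat analysis secondary, then states: "A Repeated measures ANOVA analysis will be used for continuation of breastfeeding". The next sentence moves to secondary outcomes. Section 13.1 names no other method for this outcome.

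Section 13.2 restates the non-inferiority aim for the 8-week proportion and sets a 15% margin. Immediate insertion counts as non-inferior "if the difference in rate with immediate insertion is no more than 15% worse than with standard insertion". The error rate and the test appear only in the sample-size sentence, "with a 1-sided Type 1 error of 5% utilizing the Z test (unpooled) 62 participants are required", which section 5.3 repeats. Section 7.1 gives the longer-term effect on breastfeeding its own method, a survival analysis.

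**The concern.** Read in order, section 13.1 assigns the ANOVA to the primary outcome. The sentence stands between the choice of analysis sets and the secondary outcomes, and it uses the term that the protocol uses elsewhere for the primary endpoint. The standard tests from that model (group, and group by time) ask whether the arms differ across visits. They include no margin, do not single out week 8, and assume a continuous response. The visits that would enter the model are not stated.

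Section 13.2 has the right ingredients but does not turn them into an instruction. It does not say whether the 15% applies to the estimated difference or to its confidence limit.

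What is at stake is the decision rule for the one hypothesis that the trial is powered for. Two analysts following the text could reach opposite conclusions from the same data.

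**Working it through.** **Inputs from the plan.** Standard-arm discontinuation 30% (5.3, 13.2). Margin 15%, read as percentage points because the rule is on a difference in rates (13.2). One-sided 5%, unpooled Z test, 80% power, 62 per arm (5.3, 13.2). Goal of 75 per arm (3.1, 5.3). Ceiling of 200 enrolled (5.3), taken as 100 per arm.

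**Not in the plan.** The expected immediate-arm rate. Both 30% and 25% are shown.

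**1. The plan's own figure.** With discontinuation rates pS (standard) and pI (immediate),

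n per arm = [pS(1−pS) + pI(1−pI)] × (1.645 + 0.842)² / (0.15 − (pI − pS))²

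- pI = 30%: (0.21 + 0.21) × 6.18 / 0.15² = 115.4, so 116.
- pI = 25%: (0.21 + 0.1875) × 6.18 / 0.20² = 61.4, so 62.

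The stated 62 therefore follows from a margin test if the immediate arm is assumed 5 points better, which the plan does not say. That is a separate finding. Here it matters only because the trial was evidently sized for a margin test.

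**2. One data set, three readings.** The count nearest 30% of 62 is 19 (30.6%). Suppose 25/62 (40.3%) in the immediate arm are not breastfeeding.

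- Difference = 6/62 = 9.7 points.
- SE = √(0.3065 × 0.6935/62 + 0.4032 × 0.5968/62) = 0.0855.
- Test of no difference at week 8: z = 0.0968/0.0855 = 1.13, two-sided p = 0.26. This stands in for any difference test. The ANOVA itself would pool visits, so its p-value cannot be derived from the plan.
- Upper limit of the two-sided 90% interval: 9.7 + 1.645 × 8.55 = 23.7 points.

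The result is non-significant and under 15 as observed, yet the limit is far above 15.

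**3. Where each rule stops**, with 19/62 in the standard arm:

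| Immediate arm | Difference (points) | Upper 90% limit (points) | Limit below 15 | Observed difference at most 15 |
|---|---|---|---|---|
| 19/62 | 0.0 | 13.6 | yes | yes |
| 20/62 | 1.6 | 15.3 | no | yes |
| 28/62 | 14.5 | 28.7 | no | yes |
| 29/62 | 16.1 | 30.3 | no | no |

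**4. False claims at the margin.** Exact binomial sums with a true 45% against 30% not breastfeeding:

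| Per arm | Confidence-limit test | Rule on the observed difference |
|---|---|---|
| 62 | 5.0% | 51% |
| 75 | 4.9% | 52% |
| 100 | 4.7% | 53% |

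Only the first column agrees with the 5% in the sample-size sentence.

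**5. Power of the confidence-limit test**, same method:

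| Per arm | Immediate arm 30% | Immediate arm 25% |
|---|---|---|
| 62 | 57% | 81% |
| 75 | 64% | 87% |
| 100 | 75% | 94% |

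**The case against.** The strongest answer is that section 13.2 already supplies the test. It stands under Data Analysis and introduces itself as covering both sample size and the analysis plan. In one paragraph it gives the 8-week proportion, the margin, the direction, a one-sided 5% error and the unpooled Z test. A statistician would infer a margin test from it. The ANOVA sentence could then belong to the repeated series in section 3.1, since it names no week, whereas section 14 adds the week when it means the primary outcome.

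Much of this stands. The two sections can be read consistently, and a rule on the point estimate conflicts with the 5% error rate in the sentence that follows it, so that reading is possible but not favoured. It is also true that a repeated-measures model can be made to yield a week-8 contrast with an interval. The criticism is of the standard tests and of ANOVA for a yes/no response.

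It does not close the gap. Sections 1.2.1 and 7.1 use continuation for the primary outcome, and section 7.1 already gives longer-term follow-up a different method. No sentence limits the ANOVA to the series or assigns the Z test to the primary endpoint.

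A reader might go further and infer that the plan has no margin test in mind, or that a non-significant ANOVA would be reported as non-inferiority. The documents do not support either. The margin and the Z test are in section 13.2, and nowhere is non-significance made the criterion. A false-claim rate for the ANOVA would need an assumed breastfeeding curve, a choice of visits and that unstated criterion, so none is given here.

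**Conclusion.** The point holds as an unreconciled conflict between sections 13.1 and 13.2. The one method named for continuation of breastfeeding does not test the 8-week non-inferiority hypothesis, the test that does is named only for sizing, and the worded rule leaves open whether the estimate or its limit is compared with the margin.

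The size depends on the reading. Under the inferred margin test, the error rate is about 5%, as intended. Under the observed-difference reading it is about 51-53% at 62 to 100 per arm. These figures rest on the plan's 30% and on 15% meaning percentage points. Because this is the trial's only powered hypothesis, the rule should be settled before the arms are compared, and section 14 already schedules quarterly preliminary analyses of this outcome.

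**What to change.** Add to section 13.1: the primary analysis is the difference (immediate minus standard) in the proportion not breastfeeding at 8 weeks, with an unpooled two-sided 90% confidence interval; non-inferiority is concluded if the upper limit is below 15 percentage points; the result is reported in the per-protocol and intention-to-treat sets already planned.

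The ANOVA sentence need not be deleted. Limit it to a supportive analysis of the 2, 4, 8, 12 and 24 week series, using a model for binary data, and state which visits enter.

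The cost is wording. Data collection does not change, and the margin, error rate and test are the plan's own. The downside to state openly is power: the plan gives no immediate-arm rate, and the explicit rule has 57%, 64% and 75% power at 62, 75 and 100 per arm if that rate is 30%, or 81%, 87% and 94% if it is 25%. The sample size needs its own correction.

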## 2. Background

### 2.1. Regarding primary objectives:

Counseling and provision of postpartum contraception is an integral component of comprehensive reproductive healthcare. A woman's preference for contraception is paramount; early initiation of postpartum contraception may assist in optimal birth spacing promoting the wellbeing of mother and baby (1). Equally important is the provision of appropriate support for breastfeeding (1). Exclusive breastfeeding for six months with continuation beyond one year of age is recommended by the American Academy of Pediatrics (AAP) (2), American Academy of Family Physicians (3), American College of Obstetricians and Gynecologists (ACOG) (4), and the World Health Organization (WHO) (5). In the United States, approximately 47% and 25% of women breastfeed exclusively at three and six months respectively, and 57% and 36% of women who supplement with formula continue breastfeeding at three and six months respectively (6).

Current recommendations advise against use of combined hormonal contraceptives in the first 4-6 weeks postpartum due to the hypercoagulable state of pregnancy and the high risk for thrombogenic events (7). Progestin-only hormonal contraceptive methods are considered appropriate for initiation in the postpartum period including the ENG subdermal implant, the levonorgestrel intrauterine device (LNG IUD), and the depot medroxyprogesterone acetate injection (8). However, because lactogenesis is precipitated by progesterone withdrawal after placental expulsion, early initiation of progestin-containing

**PROTOCOL TITLE:** Effect of immediate versus standard postpartum insertion of the contraceptive implant on breastfeeding outcomes

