## 7. Study Endpoints

	Screen -ing	First 24 hours Post partu m	1-7 days*	2 weeks	4 weeks	6 weeks	8 weeks	12 weeks	24 weeks END	Up to 1 year pp	Up to 5 years pp
Intake	X										
Postpartum contraception counseling satisfaction survey	X				X						
Device Insert		X			X	X					
Exclusive breastfeeding			X	X	X		X	X	X		
Breastfeeding discontinuation				X	X		X	X	X		
Retrospective Breastfeeding Discontinuation Chart Review Form										X	
Contraceptive use			X		X		X	X	X		X
Diary collection				X	X		X				
Mood (EPDS)				X	X		X				
Sexual function (FSFI)					X		X	X			
Bleeding log review				X	X		X				

7.1. The primary endpoint of this research are to compare continuation of lactation at eight week postpartum between women in the immediate with standard group.

The secondary endpoints of this research are to compare number of days of postpartum bleeding, postpartum sexual function as measured by FSFI score, and postpartum mood as measured by EPDS score, time to resumption of sexual activity, exclusive breastfeeding method, factors associated with discontinuing breastfeeding, timing of breastfeeding discontinuation, patient satisfaction with postpartum contraception counseling and the implant and patient satisfaction with bleeding pattern between the immediate and standard insertion groups.

As in other studies of breastfeeding and hormonal contraception, we will continue to follow women out to 6 months. A survival analysis will be performed to determine longer-term effect of hormonal contraception on breastfeeding.

**PROTOCOL TITLE:** Effect of immediate versus standard postpartum insertion of the contraceptive implant on breastfeeding outcomes

- 7.2. The primary study endpoint is also a safety endpoint: breastfeeding continuation through 8 weeks. We have developed a Data Safety and Monitoring Plan related to these endpoints (please see below).
- 7.3. No exploratory endpoints will be conducted in this research.

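### Section 13.1 lists two right-censored breastfeeding durations under tests that take no account of censoring, and does not carry through the survival analysis promised in section 7.1

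*Combined protocol and SAP*

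**What the plan says.** Section 13.1 (Data Analysis) states that for secondary outcomes "we will use the T-test, Wilcoxon Rank Sum test, Chi-squared test" or Fisher's exact test, as appropriate. The next sentence lists those outcomes. It begins "Secondary outcomes to be evaluated are to compare time of exclusivity of breastfeeding" and goes on to "time of breastfeeding discontinuation and patient satisfaction with postpartum contraception counseling". Where groups differ, "multivariable linear (for continuous outcomes) and logistic (for dichotomous outcomes) regression will be utilized in addition to control for confounding". Section 13 names no time-to-event method and gives no rule for a woman still breastfeeding at her last contact.

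Section 7.1 (Study Endpoints) lists timing of discontinuation among the secondary endpoints, notes that women are followed to six months, and adds: "A survival analysis will be performed to determine longer-term effect of hormonal contraception on breastfeeding". It gives no estimator, test, censoring rule or endpoint definition.

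Secondary Objectives 4 and 6 (section 1.3) concern exclusive breastfeeding and timing of discontinuation through six months. Follow-up is 24 weeks (section 6.1). Section 2.1 reports that nationally "57% and 36% of women who supplement with formula continue breastfeeding at three and six months respectively".

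**The concern.** A duration of breastfeeding is fully observed only for women who stop while under follow-up. For everyone else the plan will know only that it exceeded some time. Of the four tests named, only the t-test and Wilcoxon suit a duration, and both need one number per woman. The analyst would have to invent a value for women still breastfeeding at 24 weeks and for women lost or withdrawn earlier, or leave them out. The plan does not say which.

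The choice matters most if early loss differs between arms. Section 15.1 withdraws women who do not have the implant placed, and section 15.2 ends data collection at removal but keeps the data already collected. The immediate arm is treated in hospital, whereas the standard arm must return at 4-6 weeks, and section 2.3 (item 7) notes that many women miss postpartum follow-up. Shortened durations could therefore enter one arm more than the other. With two sections naming different methods for breastfeeding duration, the method could also be chosen after the results are seen.

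**Working it through.** The plan gives no power or precision figure for these outcomes, so there is none to reproduce. The check asks how much censoring to expect and what it does to the named tests.

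**1. Share censored at the end of follow-up**
- Any breastfeeding at six months: 36% (section 2.1; a national figure for women who supplement).
- Cross-check from the plan's 30% stopped by 8 weeks (section 13.2), assuming a constant hazard: 0.70^(24/8) = 0.70^3 = 34%.
- Exclusive breastfeeding at six months: 25% nationally (section 2.1), 27.6% in New Mexico (section 2.3, item 4).
- In addition, 20% expected loss (section 13.2).

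**2. Assumptions for the comparison.** Exponential times; 75 per arm (the enrolment goal in section 5.3); two-sided 5%, since the plan states no level for secondary tests; exact stopping times. Alternative: 30% (standard) versus 45% (immediate) stopped by 8 weeks.
- Hazard ratio = ln(0.55)/ln(0.70) = 1.68.
- Mean times 1/λ, with λ = -ln(0.70)/8 and -ln(0.55)/8: 22.43 and 13.38 weeks.
- Restricted mean to 24 weeks = (1 - S(24))/λ: 22.43 × (1 - 0.343) = 14.74 and 13.38 × (1 - 0.166) = 11.16. The difference is 3.58 weeks.

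**3. Simulated rejection rates (3,000 runs each).** Capped means that continuers are set to 24 weeks and lost women to their last contact.

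| Scenario | Log-rank | Wilcoxon, capped | t-test, capped | Mean difference, capped (standard minus immediate) |
|---|---|---|---|---|
| Alternative, no loss | 78% | 74% | 74% | 3.59 weeks |
| Alternative, 20% loss in each arm | 74% | 61% | 63% | 3.14 weeks |
| Alternative, loss 30% standard / 10% immediate at 4-8 weeks | 73% | 17% | 17% | 1.39 weeks |
| No difference, no loss | 5% | 5% | 5% | 0.03 weeks |
| No difference, 20% loss in each arm | 5% | 5% | 5% | 0.01 weeks |
| No difference, loss 30% / 10% at 4-8 weeks | 5% | 25% | 27% | -1.91 weeks |

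Repeat runs of the second row ranged from 74% to 77% for log-rank and from 61% to 65% for the other two tests.

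**4. Closed-form checks of the capped differences**
- Equal 20% loss, uniform over 0-24 weeks. For a lost woman the expected capped time is (1/λ)(1 - restricted mean/24): 22.43 × (1 - 14.74/24) = 8.66 and 13.38 × (1 - 11.16/24) = 7.16, a difference of 1.50. Overall: 0.8 × 3.58 + 0.2 × 1.50 = 3.16 weeks.
- No true difference, loss uniform over 4-8 weeks. The expected capped time for a lost woman is 22.43 × (1 - 0.766) = 5.24 weeks, where 0.766 = (0.837 - 0.70)/(4 × 0.0446) is the average of S over 4-8 weeks. Each lost woman is shortened by 14.74 - 5.24 = 9.50 weeks on average. Extra loss of 20 points in the standard arm gives 0.2 × 9.50 = 1.90 weeks of spurious advantage to immediate insertion, matching the last row.

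**5. Discontinuers only.** If all censored women were left out, power under the alternative would be 16-17% with 20% loss in each arm, and the difference would appear as 1.25 weeks.

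**The case against.** Section 7.1 goes some way to meeting the point. It names timing of discontinuation as an endpoint and then promises a survival analysis of breastfeeding to six months, so the link to Secondary Objective 6 is fairly plain. Section 13.1 offers a general menu to be used as appropriate and maps no test to any outcome. Secondary Objective 4 could be analysed as the proportion exclusively breastfeeding at each visit, where chi-squared is valid. Section 12 also provides retrospective surveys and chart review up to one year, which may recover some of the 20% loss. All of this stands. What it leaves open is the missing method and censoring rule in section 13, and exclusivity as a duration, which 13.1 lists and 7.1 does not cover.

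A reader might infer that 13.1 contradicts 7.1. The text supports only that the two are unreconciled. A reader might also infer that women still breastfeeding will be dropped, so that power falls to about 15%. That is the worst case, and the plan nowhere says it. Nor do the documents give a third still breastfeeding as an expectation for this trial. The 36% is a national figure for women who supplement, and for exclusivity the corresponding share is about a quarter. Finally, section 1.3 states no-difference hypotheses for Secondary Objectives 1 to 3 only, so no such hypothesis can be attributed to Objectives 4 and 6.

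**Conclusion.** The point holds as a gap in the analysis of two secondary outcomes. Bias is conditional, not automatic. With equal loss and capped times, the named tests keep their 5% error under no difference. Their cost is moderate: power of 61-65% against about 75% for log-rank, and a 3.6-week difference shown as about 3.2. With unequal early loss the damage is serious: about 25-27% type I error against 5% for log-rank and, if the standard arm loses more, an apparent advantage for immediate insertion that does not exist.

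These sizes rest on exponential times, 75 per arm, a two-sided 5% level, and loss unrelated to feeding. The 30% versus 10% loss is an assumption chosen to show the mechanism; the plan gives only 20% overall. If withdrawal is itself related to feeding, log-rank is not protected either. The primary endpoint at 8 weeks is not affected.

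**What to change.** In section 13.1, take the two durations out of the t-test/Wilcoxon list. State that each is analysed by Kaplan-Meier curves with a log-rank test and a Cox hazard ratio, or the difference in restricted mean time to 24 weeks, with a 95% confidence interval. Censor at the last date on which feeding status is known, and cross-reference section 7.1 so that the two sections name one method. Say explicitly that this covers exclusivity as well as any breastfeeding, and use the Cox model for any adjusted analysis of these two outcomes.

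Add two refinements. The data collection table in section 12 lists continuation at 2, 4, 8, 12 and 24 weeks but no stopping date. If only visit status is recorded, use an interval-censored method, at least as a sensitivity analysis, because the last gap is 12 weeks wide. Also add a sensitivity analysis for possibly informative withdrawal after non-insertion or removal.

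The cost is a few sentences and slightly more analysis work. No new data are needed.
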